##### **4.3.1.1 Fluid Biomarker Endpoints**

Fluid Biomarker endpoints include:

- Change from Baseline to Months 6, 12, 18, 24, 30, and 36 in NfL and other exploratory marker(s) (e.g., GFAP) in blood

- Change from Baseline to Months 12, 24, and 36 in sTREM2, sCSF1R, NfL and other exploratory marker(s) (e.g., GFAP, Osteopontin) for the CSF Population

#### **4.3.1.2 MRI Endpoints**

MRI parameters will all be listed, and parameters will be summarized by Visit, Subject and Subgroup. Listings will include Visit, observed values, change from baseline value and percent change from baseline values. Descriptive statistics (number, arithmetic mean, SD, minimum, median, and maximum) will be presented by Population and Subgroup.

Data from the retrospective pre-screening MRIs are not included with the MRI analysis.

MRI endpoints include:

- Change from Baseline to Months 6, 12, 18, 24, 30, and 36 in regional brain volume measures (ventricle volume, total gray matter volume, whole brain volume, corpus callosum thickness, corpus callosum volume, white matter lesions and brain volume composite)
- Change from Baseline to Months 6, 12, 18, 24, 30, and 36 in ALSP MRI Severity Score

#### **4.3.2 Clinical Outcome Endpoints**

The following endpoints will be analyzed to determine change over time within the Study Population and if changes from baseline differ across the Subgroups.

Descriptive statistics (as described in [Section 4.1.7](#)) will be presented by Subgroup for observed, change from baseline, and percentage change from baseline, where appropriate.

##### **4.3.2.1 Cognitive Assessments**

- Change from Baseline to Months 6, 12, 18, 24, 30, and 36 in the MoCA
- Change from Baseline to Months 6, 12, 18, 24, 30, and 36 in the CDR®+NACC-FTLD Global Score and Sum of Boxes Score
- Change from Baseline to Months 6, 12, 18, 24, 30, and 36 in the CBFS Motor, Non-motor, and Total Score

##### **4.3.2.2 Motor Assessments (Ambulatory Subjects)**

- Change from Baseline to Months 6, 12, 18, 24, 30, and 36 in the 2MWT
- Change from Baseline to Months 6, 12, 18, 24, 30, and 36 in the TUG test

#### **4.3.2.3 Severity of Illness Assessments**

- CGI-C at Months 6, 12, 18, 24, 30, and 36
- PGI-C at Months 6, 12, 18, 24, 30, and 36
- Shift tables for CGI-S at Baseline to CGI-C at Months 6, 12, 18, 24, 30, and 36
- Shift tables for PGI-S at Baseline to PGI-C at Months 6, 12, 18, 24, 30, and 36

#### **4.3.2.4 Other Functional and Psychiatric Assessments (Caregiver Population)**

- Change from Baseline to Months 6, 12, 18, 24, 30, and 36 in the FAQ Score
- Change from Baseline to Months 6, 12, 18, 24, 30, and 36 in the NPI-12 Total Score
- Change from Baseline to Months 6, 12, 18, 24, 30, and 36 in the CBFS Motor, Non-motor, and Total Score
- Change from Baseline to Months 6, 12, 18, 24, 30, and 36 in the Total ZBI Score

#### **4.3.3 Exploratory Endpoints**

Exploratory endpoints were added to this SAP, but not to the main study protocol, to help facilitate an integrated analysis of this NHS as a control group compared to a Phase 2 study with a treated population. The outcomes below are not included in study protocol v5.0. The third study objective in the protocol is to create the foundation for a future synthetic control arm, and the exploratory endpoints are consistent with meeting that aim.

#### **4.3.4 Repeated Measures Analysis**

Mean changes from baseline in Ventricle Volume, MoCA, and CBFS will be analyzed using restricted maximum likelihood-based mixed effects models for repeated measures (MMRM). Separate models will be generated that consider study visit as a categorical variable, and study day as a continuous variable.

In addition the analyses described below, exploratory analyses may be conducted in which additional covariates are added to the previously described MMRM analyses to understand the influence of these covariates and how imbalance in them across may have influenced results. Additionally, if meaningful outliers are identified by the descriptive analyses, the corresponding MMRM analyses may be replicated as a sensitivity analyses in which the outlier observation(s) is omitted.

MMRM analyses may also be performed with percent change from baseline as the dependent variable for the MRI and biomarker endpoints.

Specifically, the following MMRM models will be explored as the primary models of interest:

- Mean change from baseline to last follow-up in Ventricle volume
- Mean changes from baseline to last follow-up in MoCA
- Mean changes from baseline to last follow-up in CBFS

#### 4.3.4.1 MMRM with Visit as a Categorical Variable

The MMRM model will assess changes from baseline as the dependent variable and include the following parameters:

- ***Subgroup (categorical variable):*** Prodromal, Symptomatic ALSP subjects (Non-HSCT), Symptomatic ALSP (Prior HSCT).
- ***Visit (categorical variable):*** Corresponding to the set of post-baseline scheduled visits for the endpoint as defined in the schedule of assessments.
- ***Baseline score (continuous variable):*** The corresponding baseline value for the dependent variable.
- ***Subgroup × Visit Interaction Effect***
- ***Baseline score × Visit Interaction Effect***

The within-subject covariance will be modeled using a compound symmetric with heterogeneous variance structure (TYPE = CSH). If this analysis fails to converge a simpler compound symmetric structure will be used (TYPE = CS). If this analysis fails to converge the baseline score by visit interaction will be deleted from the model. Denominator degrees of freedom will be determined using the Kenward-Roger approximation.

For each of the 3 subgroups defined above for the categorial Subgroup variable, least squares mean with corresponding SEs, lower and upper bounds of the 95% confidence interval, and p-values will be reported for the within group changes from baseline. The least squares mean difference from the Prodromal subgroup will be similarly presented. Additionally, least squares means and least squares mean difference (versus Prodromal) statistics for the Symptomatic ALSP subgroup (i.e., estimated using a weighted average of the Symptomatic ALSP (Non-HSCT) and Symptomatic ALSP (Prior HSCT) subgroups) may also be estimated.

For each MMRM analysis, a figure will be produced which depicts the least squares mean changes from baseline along with the SE for each of the 3 subgroups by visit.

Sample SAS® code for an MMRM model with study visit as a categorical variable is as follows:

```
PROC MIXED DATA = ADEFF;
  CLASS SUBGR1 (REF='PRODROMAL') AVISIT (REF='BASELINE');
  MODEL CHG = SUBGR1 AVISIT BASE SUBGR1*AVISIT BASE*AVISIT /
  DDFM=KR;
```

```
REPEATED AVISIT / SUBJECT=USUBJID TYPE=CSH;  
LSMEANS SUBGR1*AVISIT / DIFF=ALL CL ALPHA=0.05;  
RUN;
```

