#### **4.1.4 Sample Size and Power**

The sample size of approximately 60 subjects was determined without a formal power calculation and is expected to provide sufficient information to address the study objectives in this rare disease.

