#### **4.1.5 Level of Significance**

Unless otherwise noted, all statistical tests will be two-sided with a significance level of 0.05. P-values greater than or equal to 0.001, in general, will be presented to three decimal places. P-values less than 0.001 will be presented as “<0.001”; p-values greater than 0.999 will be

presented as “>0.999”. Confidence intervals will be presented to one more decimal place than the point estimate.

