#### 4.1.10 Study Visit

Scheduled subject visits (i.e., Screening/Baseline, Month 6, Month 12, Month 18, Month 24, Month 30, Month 36) will be determined by the visit as specified in the eCRF. That is, scheduled visits will not be windowed and the nominal visit value will be used for analysis.

To utilize as much data as possible for analysis, unscheduled and ET visits will be mapped to a scheduled visit for analysis using windows as defined below, which are to be used for analysis purposes only. Once analysis visit windows are assigned, all visits, including unscheduled and ET visits, are eligible to be flagged as the “analyzed record” within the analysis window. As such, a subject may have more than one record for each analysis visit window. The following rule for determining which record is flagged as the “analyzed record” is as follows:

- When available, data from the scheduled visit is always used.
- If data from the scheduled visit is not available, then data from the unscheduled or ET visit closest to the scheduled visit study day for that analysis window will be used, if available.

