#### 4.3.4.2 MMRM with Study Day as a Continuous Variable

The MMRM model will assess changes from baseline as the dependent variable and include the following parameters:

- **Subgroup** (categorical variable): Prodromal, Symptomatic ALSP subjects (Non-HSCT), Symptomatic ALSP subjects (Prior HSCT)
- **Study Day** (continuous variable)
- **Subgroup × Study Day** (interaction)

Within subject errors will be modeled using an unstructured covariance matrix. Denominator degrees of freedom will be determined using the Kenward-Roger approximation. If this analysis fails to converge, Heterogeneous Toeplitz, Heterogeneous Auto-regressive, and Heterogeneous Compound Symmetric structures will be tested. The first structure to yield convergence will be considered the primary analysis for each respective dependent variable.

For each of the 3 subgroups (i.e., as defined above for the categorial Subgroup variable), estimated change from baseline values at Months 6, 12, 18, 24, 30, and 36 will be presented with corresponding SEs, lower and upper bounds of the 95% confidence interval, and p-values will be reported for the within group changes from baseline. The difference from the Prodromal subgroup will be similarly presented for the Months 6, 12, 18, 24, 30, and 36 estimates. Additionally, values at Months 6, 12, 18, 24, 30, and 36 for the Symptomatic ALSP subgroup (i.e., estimated using a weighted average of the Symptomatic ALSP (Non-HSCT) and Symptomatic ALSP (Prior HSCT) subgroups) and corresponding difference from the Prodromal subgroup may also be estimated.

For each MMRM analysis, a figure will be produced which depicts the regression lines for each of the subgroups with the SE of the estimate being presented at Months 6, 12, 18, 24, 30, and 36.

Sample SAS® code for an MMRM model with study day as a continuous variable is as follows:

```
PROC MIXED DATA = ADEFF;  
  CLASS USUBJID SUBGR1 (REF='PRODROMAL') ;  
  MODEL CHG = SUBGR1 ADY SUBGR1*ADY / DDFM = KR;  
  REPEATED / SUBJECT = USUBJID TYPE = UN;  
RUN;
```

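### SAP 4.3.4.1: the text restricts the visit MMRM to post-baseline visits, but the sample code names BASELINE as the reference visit; if baseline rows with zero change enter, the planned covariance model has no solution

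*SAP*

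**What the plan says.** Section 4.3.4.1 of the SAP defines the outcome: "The MMRM model will assess changes from baseline as the dependent variable". It then defines the visit factor: "Corresponding to the set of post-baseline scheduled visits for the endpoint as defined in the schedule of assessments". With the SAP's schedule that is six levels, Months 6 to 36.

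The sample code in the same section opens with "PROC MIXED DATA = ADEFF", with no record selection, and continues with "CLASS SUBGR1 (REF='PRODROMAL') AVISIT (REF='BASELINE". It indexes the within-subject covariance by the same visit variable. The planned structure is CSH. If that fails to converge, CS is used, and if CS also fails, the baseline-by-visit term is dropped.

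A baseline value of the visit variable does exist in the analysis data. Section 4.1.10 lists it among the scheduled visits ("Scheduled subject visits (i.e., Screening/Baseline, Month 6, Month 12, Month 18, Month 24, Month 30, Month 36) will be determined by the visit as specified"), and Table 2 gives it an analysis window. The SAP nowhere says whether the change variable is set to 0 or left missing on that record.

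Section 4.3.4.2, the study-day model, has the class statement "CLASS USUBJID SUBGR1 (REF='PRODROMAL" and no visit factor. It names no baseline level, but neither its text nor its code excludes baseline records.

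**The concern.** A change-from-baseline value at baseline is a structural zero, not an observation. The text leaves such rows out; the code names them as the level against which the others are set. Both cannot be right, and under the independent double programming required by SAP 4.1.3 one programmer could follow the text and the other the code.

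At stake is the covariance model, and hence every standard error, confidence interval and p-value, for the analyses that SAP 4.3.4 singles out as its main models: ventricle volume, MoCA and CBFS. SAP 4.3.3 links the added exploratory endpoints to use of this study as a control group for the Phase 2 study, so the precision attached to these estimates matters beyond this report.

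**Working it through.** The plan gives no standard error or power figure to reproduce ("The sample size of approximately 60 subjects was determined without a formal power calculation").

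**Inputs from the SAP.** About 60 subjects; three subgroups; six post-baseline visits; 95% intervals ("all statistical tests will be two-sided with a significance level of 0.05"); CSH, then CS.

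**Assumptions, not in the documents.** Subgroups of 15 prodromal, 38 symptomatic non-HSCT and 7 prior HSCT. Within-subject correlation 0.6. Either a constant SD of 4, or an SD rising in equal steps from 2 at Month 6 to 6 at Month 36. Attrition either none, 10 percentage points per visit, or steeper. Baseline change stored as 0.

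**Step 1: CSH with zero rows.** At the baseline visit the model has 4 fixed effects (three subgroup means and one baseline slope). They fit the 60 zeros exactly. The baseline variance can therefore shrink without penalty, and -2 REML falls by 2 x (60 - 4) x ln 10 = 258 for each tenfold drop in the baseline SD. Evaluated directly, it was 671, 413, 155, -103 and -360 at SDs of 1, 0.1, 0.01, 0.001 and 0.0001. There is no optimum. A free optimiser drove the SD to about 1e-33 and then met a singular matrix.

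**Step 2: CS with zero rows against CS without.** With complete data, CS averages the visit variances. Adding one zero row to m = 6 multiplies the pooled variance by 6/7, so the SE ratio is sqrt(6/7) = 0.926. Check for symptomatic non-HSCT minus prodromal, constant SD: 4 x sqrt(1/15 + 1/38) = 1.22, and 1.22 x 0.926 = 1.13, as simulated. With attrition the simulated ratio was 0.85 to 0.96 (250 runs per cell). Under constant variance and 10 points of attrition per visit, average coverage fell from about 95% to about 91%. Intervals used 2.0 x SE, not Kenward-Roger.

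**Step 3: CS with zero rows against the planned CSH without them.** Average ratio of SEs over 80 runs per row:

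| True variance | Attrition | M6 | M12 | M18 | M24 | M30 | M36 |
|---|---|---|---|---|---|---|---|
| Constant | none | 0.93 | 0.93 | 0.94 | 0.93 | 0.94 | 0.93 |
| Constant | 10 points/visit | 0.86 | 0.87 | 0.90 | 0.90 | 0.91 | 0.95 |
| Growing | none | 1.98 | 1.43 | 1.10 | 0.88 | 0.75 | 0.66 |
| Growing | 10 points/visit | 1.66 | 1.17 | 0.94 | 0.78 | 0.68 | 0.63 |

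The growing case with complete data can be checked by hand. The squared SDs (2, 2.8, 3.6, 4.4, 5.2, 6) sum to 107.2, and sqrt(1/15 + 1/38) = 0.305.
- CSH: 2 x 0.305 = 0.61 at Month 6 and 6 x 0.305 = 1.83 at Month 36.
- CS without zeros: sqrt(107.2/6) x 0.305 = 1.29 at every visit.
- CS with zeros: sqrt(107.2/7) x 0.305 = 1.19 at every visit (simulated: 1.19).

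Most of the distortion here is the forced move from CSH to CS; the zeros then take off a further 7%.

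**Step 4: the study-day model.** Its candidate structures (unstructured, then heterogeneous Toeplitz, autoregressive and compound symmetric) each give the first record its own variance. If zero rows entered at Day 1, three subgroup values would fit them exactly, and -2 REML would fall by 2 x (60 - 3) x ln 10 = 262 per tenfold drop in that SD. Spreading the baseline rows over earlier days does not help: lines with zero intercept and slope still fit them exactly. No homogeneous structure is listed as a fallback.

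**The case against.** The code is labelled as a sample. It also omits the endpoint selection and the analysed-record flag that any real run needs, so the absence of a filter does not show that baseline rows will enter. That stands; the positive evidence is the named reference level alone. The prose is explicit, the programming is to be verified independently, and the least-squares means output would show a visible baseline row. These make a silent error less likely, but they do not say which of two conflicting specifications governs.

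Four stronger readings are tempting and not supported.

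- A reader might infer that the intervals for these models will in general be too narrow. That holds against CS without the rows, and against CSH only when variances are roughly constant. By planning CSH the SAP itself allows variances to differ by visit, and with growing variance the early standard errors are too large.
- A reader might infer that the planned covariance is certain to be lost. That requires baseline change stored as 0, which the SAP does not settle. If it is missing, the rows drop out.
- A reader might infer that the software will always report non-convergence and move to CS. SAS was not run. In a small check (12 runs per setting, constant variance), a CSH fit held at a baseline SD of 0.001 gave standard errors about three times too large, the opposite direction.
- A reader might infer that 4.3.4.2 contains the same error. It names no baseline level and reports estimates only at Months 6 to 36. It merely fails to exclude the rows.

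**Conclusion.** Wrong as written: the text and the sample code of 4.3.4.1 specify different models, and the SAP leaves open the one fact, how change is stored at baseline, that decides whether this does harm.

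If it is stored as missing, what remains is an inconsistency to correct. If it is stored as 0 and the rows enter, the planned CSH model cannot be validly fitted; that result needs no assumption about variances or attrition. The size of the error under the CS fallback does depend on them: about 7% with complete data and roughly 4-15% with attrition relative to CS without the rows, and anything from about twice to about 0.63 times the planned CSH standard error when the SD grows threefold over follow-up. The subgroup sizes, SDs, correlation and attrition behind these figures are assumed. For 4.3.4.2 the conclusion is only that baseline records should be excluded explicitly.

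**What to change.** In both programs, restrict the input to post-baseline records flagged as the analysed record for the endpoint being modelled. The flag is needed anyway, because SAP 4.1.10 allows several records per window.

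In 4.3.4.1, remove `REF='BASELINE'`. Any post-baseline reference level, or none, gives the same least-squares means; removing the rows is what corrects the model, and changing the reference alone would not.

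State in both sections that baseline records are excluded, and how change is stored at baseline.

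A minor tidy-up: add `USUBJID` to the class statement in 4.3.4.1, as 4.3.4.2 already does.

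The cost is a few lines of code and one sentence in each section. It agrees with the model text already in 4.3.4.1 and gives up no post-baseline analysed data.

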#### 4.3.4.2 MMRM with Study Day as a Continuous Variable

The MMRM model will assess changes from baseline as the dependent variable and include the following parameters:

- **Subgroup** (categorical variable): Prodromal, Symptomatic ALSP subjects (Non-HSCT), Symptomatic ALSP subjects (Prior HSCT)
- **Study Day** (continuous variable)
- **Subgroup × Study Day** (interaction)

Within subject errors will be modeled using an unstructured covariance matrix. Denominator degrees of freedom will be determined using the Kenward-Roger approximation. If this analysis fails to converge, Heterogeneous Toeplitz, Heterogeneous Auto-regressive, and Heterogeneous Compound Symmetric structures will be tested. The first structure to yield convergence will be considered the primary analysis for each respective dependent variable.

For each of the 3 subgroups (i.e., as defined above for the categorial Subgroup variable), estimated change from baseline values at Months 6, 12, 18, 24, 30, and 36 will be presented with corresponding SEs, lower and upper bounds of the 95% confidence interval, and p-values will be reported for the within group changes from baseline. The difference from the Prodromal subgroup will be similarly presented for the Months 6, 12, 18, 24, 30, and 36 estimates. Additionally, values at Months 6, 12, 18, 24, 30, and 36 for the Symptomatic ALSP subgroup (i.e., estimated using a weighted average of the Symptomatic ALSP (Non-HSCT) and Symptomatic ALSP (Prior HSCT) subgroups) and corresponding difference from the Prodromal subgroup may also be estimated.

For each MMRM analysis, a figure will be produced which depicts the regression lines for each of the subgroups with the SE of the estimate being presented at Months 6, 12, 18, 24, 30, and 36.

Sample SAS® code for an MMRM model with study day as a continuous variable is as follows:

```
PROC MIXED DATA = ADEFF;  
  CLASS USUBJID SUBGR1 (REF='PRODROMAL') ;  
  MODEL CHG = SUBGR1 ADY SUBGR1*ADY / DDFM = KR;  
  REPEATED / SUBJECT = USUBJID TYPE = UN;  
RUN;
```

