7.2 Lost to Follow-up

A subject will be considered lost to follow-up if he or she repeatedly fails to return for scheduled visits and is unable to be contacted by the investigative site. The site must attempt to contact the subject and reschedule the missed visit as soon as possible and must counsel the subject on the importance of maintaining the assigned visit schedule and ascertain whether or not the subject wishes to and/or should continue in the study.

Before a subject is deemed lost to follow up, the investigator or designee must make every effort to regain contact with the subject (where possible, 3 telephone calls). These contact attempts should be documented in the subject's medical record. Subjects who continue to be unreachable will be considered to have withdrawn from the study.

Attempts will be made to determine the survival status (alive or deceased) of any subjects who fail to return for their study visit or who discontinue from the study before completing the 24-month (subjects who withdraw from the study before implementation of Amendment 3) or 36-month (subjects who withdraw from the study after implementation of Amendment 3) observation period. Study staff will contact the subject or the subject's study partner by telephone to determine survival status 24 or 36 months, respectively, after the date of the subject's Screening Visit or at the end of the study, whichever occurs sooner.

Discontinuation of specific sites or of the study as a whole is described in Appendix 1 ([Section 10.1.6](#)).

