#### 4.1.12 Handling of outliers

Outliers will be identified to ensure the validity and robustness of the statistical analyses. The following methods may be used to detect outliers in the dataset:

- **Data visualization:** Boxplots, scatterplots and histograms may be used to visually identify points that appear to deviate from the overall distribution.
- **Statistical criteria:** For select continuous variables, values falling more than  $+/- 3$  standard deviations above or below the mean will be flagged as potential outliers. For select categorical variables, frequencies containing  $<3\%$  of the overall data will be reviewed to identify any unusual, improbable, or implausible categories.
- **Clinical context:** Outlying data points will also be assessed in the context of clinical plausibility and data collection procedures to determine whether outliers are likely data errors or true anomalies. For example, 2-Minute Walk Test (2MWT) distances exceeding 300 meters will be excluded from analyses as these values are implausible for this study patient population (Bohannon, 2017).

Once identified, outliers may be handled by any or a combination of the following procedures:

- **Verification:** Data flagged as outliers may be cross-checked against EDC, eCRF and source records to rule out data entry errors and confirm true anomalies.
- **Documentation:** Outliers will be documented as likely data entry errors, likely valid but extreme observations, or data with an unknown cause.

For outliers that are deemed to be valid but extreme observations:

- Sensitivity analysis may be conducted with and without outliers to assess their impact on results
- Outliers will be included in the primary analysis but may be interpreted jointly with sensitivity analysis if their influence impacts the resulting conclusions and yields findings that are not robust

All decision regarding handling outliers, including their identification and inclusion/exclusion from analyses, will be documented in detail in a Statistical Report and in the CSR.

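### The study-day MMRM gives its unstructured covariance no visit index, so an absent mid-profile row moves a subject's later records to the wrong visit; name a chronological visit number as the repeated effect.

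*SAP*

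**What the plan says.** SAP 4.3.4 singles out ventricle volume, MoCA and CBFS for its main repeated-measures models. Each is fitted with visit as a category (4.3.4.1) and with study day as a continuous covariate (4.3.4.2). The study-day version supplies the regression lines and the estimates at Months 6 to 36.

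For that version the text asks for an unstructured matrix. If it does not converge, "Heterogeneous Toeplitz, Heterogeneous Auto-regressive, and Heterogeneous Compound Symmetric structures will be tested", and the first structure to converge becomes primary. The sample code is "REPEATED / SUBJECT = USUBJID TYPE = UN". The CLASS line begins "CLASS USUBJID SUBGR1 (REF='PRODROMAL" and holds no visit variable. Neither code nor text says what indexes the matrix. The categorical model in 4.3.4.1 does: "REPEATED AVISIT / SUBJECT=USUBJID TYPE=CSH".

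Three other places bear on this:
- SAP 4.3.4 allows that, if meaningful outliers are found, "the corresponding MMRM analyses may be replicated as a sensitivity analyses in which the outlier observation(s) is omitted". SAP 4.1.12 gives the purpose: "Sensitivity analysis may be conducted with and without outliers to assess their impact on results".
- SAP 4.1.10 notes that "a subject may have more than one record for each analysis visit window", and flags one of them for analysis.
- Protocol 7.2 tells sites to "reschedule the missed visit as soon as possible", so missed visits are foreseen.

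**The concern.** An unstructured matrix has a separate variance for each visit and a separate covariance for each pair of visits. With no index, only record order says which record belongs to which row. That is safe if every subject's rows are complete and in date order up to the last one. Nothing in the SAP requires a placeholder row for a visit that did not take place.

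If an intermediate row is absent, the mean model stays right because study day is still correct, but the covariance is wrong. It feeds the weights, the standard errors and the Kenward-Roger degrees of freedom. Standard errors can then be too small, and if the gaps are linked to decline the estimate is biased. An outlier rerun that drops a row would mix the outlier's own effect with this artefact.

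**Working it through.** The plan states no figure to reproduce. The check follows the records and then simulates.

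**1. Which slot each record takes under record order**

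| Absent row | Later records are treated as |
|---|---|
| Month 6 | Months 12, 18, 24, 30, 36 as Months 6, 12, 18, 24, 30 |
| Month 18 | Months 24, 30, 36 as Months 18, 24, 30 |
| Month 24 | Months 30, 36 as Months 24, 30 |
| Only the last visits (dropout) | nothing shifts |

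A row kept with a missing change score holds its place. A MoCA or CBFS score set to missing under SAP 6.2.4 is therefore harmless if its row is kept.

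**2. How a row can be absent**

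- An outlier observation is omitted in a rerun (SAP 4.3.4); on a plain reading this drops the row.
- A missed visit is never made up.
- A telephone visit has no MRI (Protocol Table 1), which affects ventricle volume only.

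The third is nearly out of reach at this interim. Assume telephone visits began with protocol 5.0 (02 Oct 2024). The freeze is on or around 11 April 2025, 191 days later. Target spacing from SAP Table 2 is 182 or 183 days, so a later scan is possible only if the call fell in the first 191 − 183 = 8 or 191 − 182 = 9 days. With both ±14-day windows fully used, this becomes 191 − 155 = 36 or 191 − 154 = 37 days. If all 60 subjects were in follow-up, 60 × 8/183 = 2.6 to 60 × 37/183 = 12.1 would have a visit in that span. If a quarter (assumed) telephoned and later returned for a scan, 0.7 to 3.0 subjects are affected.

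**3. Simulation**

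All inputs are assumed, because the documents give no SDs, slopes or gap rates: 60 subjects (12 prodromal, 42 symptomatic non-HSCT, 6 prior HSCT); slopes −0.5, −2 and −1 per year; slope SD 2; error SD 1.5; visit jitter ±14 days; 8% dropout per visit. The target is the symptomatic (non-HSCT) change at Month 36, −2 × 3 = −6.0. Each dataset was fitted by REML with Kenward-Roger, once by record order (as coded) and once by visit index. Monte Carlo error of coverage is about 1 percentage point.

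- *Trailing dropout only, or rows kept with missing change:* identical by construction.
- *One gap (Month 18, 24 or 30) in a few fast decliners, 400 replicates each:*

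| Subjects with a gap | Shift, as coded minus indexed | Shift as % of 6.0 (unrounded shifts) | Coverage, as coded vs indexed |
|---|---|---|---|
| 1 | −0.08 | 1.3 | 94.5% vs 94.2% |
| 2 | −0.14 | 2.4 | 95.5% vs 95.8% |
| 3 | −0.21 | 3.5 | 93.5% vs 95.0% |

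- *Intermediate rows absent at random, 600 replicates each:*

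| Probability | Subjects with a gap | Coverage, Month 36 change | Coverage, difference from Prodromal |
|---|---|---|---|
| 2% | 4.5 | 96.3% vs 95.8% | 93.2% vs 93.2% |
| 5% | 10.9 | 93.3% vs 94.3% | 92.2% vs 94.3% |
| 10% | 19.7 | 89.9% vs 93.8% | 90.9% vs 94.1% |

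At 10%, the mean SE as coded was 1.007 against an empirical SD of 1.172; indexed, 1.053 against 1.084.

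- *Bias against the true value, separate run of 200 replicates:* with three fast-decliner gaps, the as-coded estimate was off by −0.22 and the indexed one by +0.05. At 10% random gaps, mean SE and empirical SD were 0.95 and 1.27 as coded, 0.99 and 1.15 indexed.
- *Outlier row omitted (value shifted by 4 SD, row dropped), 300 replicates:*

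| Outliers | Median genuine effect | Median added by misalignment | Added at least half the genuine | Direction reversed |
|---|---|---|---|---|
| 1 | 0.122 | 0.083 | 60% | 16% |
| 2 | 0.170 | 0.117 | 62% | 17% |

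For one outlier the added shift is 0.08 SE at the median and 0.27 SE at the 95th percentile.

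**4. Why the index must be in time order**

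Sorted as text, the visit labels run Month 12, 18, 24, 30, 36, 6. This does not matter for an unstructured or compound-symmetric matrix. Under a heterogeneous autoregressive fallback with ρ = 0.8, time order gives correlations of 0.8 for Months 6 and 12 and 0.8⁵ = 0.33 for Months 6 and 36. Text order swaps them.

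**The case against.** The code is labelled as a sample and is visibly abbreviated: it does not even select one endpoint. SAP 4.1.3 requires independent programming, and the correctly indexed model in 4.3.4.1 stands beside this one. SAP 4.1.10 lets unscheduled and early-termination records fill a missed visit within windows of ±90 days, so true gaps may be few, and it already flags one record per window. The outlier rerun is optional and depends on outliers being found; valid outliers stay in the main analysis. A reversal of direction can occur only where the genuine effect is smaller than the added shift, so it mostly concerns small effects. The simulations report Month 36 without staggered entry or completion at Month 24, whereas a Month 36 record by the freeze needs a baseline by about April 2022.

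Most of this stands as to likelihood and size. The effect at this interim has not been estimated, and the 10% gap rate has no support in the documents. It does not remove the omission. The text gives no index that a programmer could use in place of the code, and two programmers following the same section can agree on the same misalignment.

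**Conclusion.** The concern holds, as a minor one. The missing index is certain from the text and code. Its effect depends on the final programs following the sample line and on intermediate rows being absent from the dataset. Under the assumed inputs, a few gaps tied to decline shift the Month 36 estimate by 1.3 to 3.5%, and coverage clearly suffers only near 10% absent rows. At this interim the effect is probably small. The firmest consequence is that a rerun with an outlier's row dropped, taken on its own, cannot show how much of the change is due to the outlier. No effect on the comparison with the Phase 2 study is claimed.

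**What to change.** In SAP 4.3.4.2, write:

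`CLASS USUBJID SUBGR1 (REF='PRODROMAL') AVISITN;`

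`REPEATED AVISITN / SUBJECT = USUBJID TYPE = UN;`

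AVISITN is a numeric analysis-visit number in time order; AVISIT with an ORDER= option that gives time order would also serve. ADY stays as the continuous fixed effect.

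Add one sentence: the chronological analysis visit is the repeated effect for the unstructured matrix and every fallback, and the model uses only the one flagged post-baseline record per subject and visit. The restriction is needed because the sample code has no filter, and extra rows would shift positions now or duplicate a visit level once the index is named. Use the same index in any outlier-omission rerun.

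The cost is one CLASS term, one REPEATED term and one sentence, with no new data. Where rows are in date order, one per visit and without intermediate gaps, results are unchanged under every listed structure.
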